### **Structure of MICM Sessions**

Participants assigned to the MICM condition will receive 3 individual sessions within the first month of entering the SLH. Thereafter they will have contact with the MICM therapist monthly throughout the duration of their enrollment in the study (12 months). However, therapists will also be available to address crises that occur, such as

psychiatric emergencies, arrests, and sudden loss of job or housing. For participants who have left the geographical area the session will be conducted by phone.

### **Comparison Condition**

The comparison condition will consist of offenders receiving SLH services as usual along with a list of resources that can be used to address a variety of problems. This will help ensure that intervention effects for MICM are not simply the result of receiving information about various services that are available in the community.

### **Pilot Testing**

We plan to test the survey measures and MICM with pilot subjects before we begin recruitment. The purpose of testing the survey is to see how respondents react to the questions, evaluate whether the questions need to be adjusted, test out the skip patterns and reliability of the online technology, and see how long the survey will take to administer. We do not plan to use the data in any of our analyses.

Some of the pilot subjects will be asked to participate in testing the MICM sessions. These subjects will meet with the therapists 1-3 times, depending on how the sessions go. The purpose of testing out the MICM is to gain a better understanding of how the intervention is received and for our therapist supervisors to ensure that the therapists are following the intervention manual appropriately and consistently. As names and contact information will be collected for some of these pilot subjects, a separate consent form will be administered.

### **Measures**

#### Baseline Only

1) DSM-IV Checklist for Lifetime and 12-Month Alcohol and Drug Abuse and Dependence. Items are based on DSM-IV diagnostic criteria (American Psychiatric Association, 2000) and have been used in NIDA Clinical Trial Network studies (Forman et al., 2004). 2) Demographic and Descriptive Characteristics. In addition to standard demographics (e.g., sex, age, race/ethnicity, and education), we ask about criminal justice history.

Instrument	Baseline	6 Months	1 Year
Baseline Only			
Lifetime DSM Checklist for X			
Alcohol/Drug Disorders			
Demographics			
Primary Outcome			
HIV Measures:	X	X	X
RAB			
HIV Status			
HIV Testing			
HIV Treatment			
Probation/Parole Violations	X	X	X
Arrests	X	X	X
Days Incarcerated	X	X	X
TLFB for Drugs and Alcohol	X	X	X
ASI Alcohol and Drug	X	X	X
Secondary Outcomes			
ASI Scales	X	X	X
Work/Income History	X		X
Housing Stability	X	X	X
Moderators/Mediators			
General Social Support	X	X	X
Social Network	X	X	X
AA/NA Involvement	X	X	X
Services Received	X	X	X
Retention	X	X	X
Confrontation (ADCS)	X	X	X
Trauma, PTSD, Abuse	X		
ADCQ	X	X	X
Biological Measures			
Urine Screen	X	X	X
Qualitative Interview			
House Environment			
SMPS			N/A

### Primary Outcomes

- 1) Criminal Justice Outcomes are taken from Petersilia (2003) and Petteruti and Walsh (2008) and include: a) Parole/Probation Violations, b) Arrests and c) Days Incarcerated. Arrests will be specified by type of offense and whether the respondent was convicted. Incarceration will be specified as due to arrest for a new offense and due to a technical violation of probation or parole. Data will be self-report but also will be confirmed using publicly available criminal justice records.
- 2) Timeline Follow-Back (TLFB) will be used to record the subject's self-report of alcohol and drug use during each interview period assessed. To maximize recall of alcohol and drug use we will assess 90-day time periods. This instrument has been used extensively in a variety of drug and alcohol studies (Sobel et al., 1996).
- 3) Four scales from the Addiction Severity Index Lite (ASI) (McLellan et al., 1992) will be used as primary outcomes. Alcohol and drug scales will be used to assess alcohol and drug severity, the legal scale will be

uses to assess legal severity and the employment scale will be used to assess employment problems. 3) The Risk Assessment Battery (RAB) (Metzger, et al, 2001) will be used to assess injection and sexual risk behaviors. An additional measure of HIV will include a count of HIV testing overall and the number who are tested for their first time. We will also record self-report of HIV status and current engagement in HIV treatment services (coded yes\no) for those who are positive.

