This application is based on the premise that probationers and parolees must have access to stable, drug free housing to reduce HIV risk, access needed services and avoid rearrests and reincarceration. Drug free housing at the Sober Living Network (SLN) in California will be studied as a way to provide a positive living environment for probationers and parolees. The houses use a sober living house (SLH) model of recovery that includes a communal recovery environment, abstinence from drugs and alcohol, peer support, and encouragement to attend self-help groups such as Alcoholics Anonymous. Preliminary data based on a sample of 300 individuals entering 20 SLHs in California showed resident improvement in a variety of areas, including drug and alcohol use, employment, psychiatric symptoms, and arrests ([name] et al., 2010). Although residents referred from parole and probation systems had substance use reductions that were comparable to voluntary residents, they had had far more problems maintaining employment, higher rates of arrest and incarceration, and lower attendance at self-help groups ([name], et al., 2010). Thirty seven percent had been rearrested at 6 month follow-up and one reason may be that probationers and parolees received only 35% of the services that they felt they needed to succeed. Although over half met DSM IV criteria for methamphetamine dependence during the last year, a very high risk group for HIV, we did not assess HIV outcomes.

The proposed study will improve SLHs for offenders by adding a Motivational Interviewing Case Management (MICM) intervention specifically targeted to the problems presented by each offender. The list of potential problems that MICM can address is extensive: 1) adapting to the SLH environment, 2) complying with parole and probation, 3) finding and maintain work, 4) successfully accessing and maintaining retention in services, 5) addressing HIV risk, testing and treatment, 6) mobilizing personal and informal resources, and 7) managing setbacks (e.g., relapse, loss of housing, loss of work).

Men and women offenders (N=330) entering SLHs will be assigned to a condition consisting of drug free housing and provision of a resources manual where residents can seek help for a variety of problems (a control group) or drug free housing plus the MICM (intervention).

**Aim 1:** To assess HIV testing rates, HIV risk behaviors, and utilization for HIV services at baseline, 6, and 12 months.

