Hypotheses H1.1 will be tested in the framework of longitudinal models, as described above. The focus is on treatment condition which, although uniquely assigned to individuals, is implemented at the house level and therefore will be treated as a level 3 variable. This allows for a limited exploratory examination of potential treatment effects with house level characteristics. Interactions of treatment condition with level 2 variables (e.g., gender) can be implemented by simply including treatment as a predictor of the non-randomly varying level 2 coefficient (e.g., gender) of interest. Evidence in favor of the hypotheses will be significant level-3 coefficients (the relevant γ coefficient) for the indicator variables (Z) representing average differences between houses in the rate of change in the outcome over time (i.e., the intercept of the level 2 slope parameter $\lambda_{o,h}$).

Aim 2: *To compare baseline substance use within each study condition with 6- and 12-month substance use.*

H2.1 Residents in each study condition will show significant reductions in drug and alcohol use between baseline and follow-up time points as measured by the Time Line Follow Back (TLFB).

H2.2 Residents in each study condition will show significant reductions in drug and alcohol problems between baseline and follow-up time points as measured by the Addiction Severity Index alcohol and drug scales.

Hypotheses H2.1 and H2.2 will be tested in the framework of longitudinal models, as described above. As a first step, an empty model will be estimated (random intercept and slope but no level 2 (individual) or level 3 (house) covariates) to test whether the variances of the intercept and slope parameters (u and v) are significant. Should significant variation be found, candidate covariates, both at the individual level (level 2) and the house level (level 3), will be considered in separate models and any such covariates will be entered as predictors of both the random intercept and slope.

Aim 3: *To compare outcomes between the two study conditions at baseline, 6, and 12 months.*

H3.1 Residents receiving MMI in addition to drug free housing will have less substance use (TLFB) and lower ASI alcohol and drug severity than the drug free housing and resources condition.

H3.2 Residents receiving MMI in addition to drug free housing will have fewer arrests, fewer days incarcerated and lower ASI legal severity than the drug free housing and resources condition.

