A second exploratory aim is to conduct 30 qualitative interviews (15 in each condition) to identify general and intervention specific factors that were perceived to affect outcomes and ways to improve the two active interventions. An initial coding list will include specific codes suggested by characteristics of the intervention. For example, codes for the SLH alone condition might include things like “helped me increase support to not use alcohol or drugs,” and “helped me avoid exposure to alcohol and drugs.” For MMI, codes might include “made suggestions for services” and “helped me prepare for living at the SLH.” For meditation, codes might include things like “helped me relax” and “increased positive feelings about myself.” Using line-by-line coding, themes and excerpts of text will be highlighted as quotations that exemplify salient resident attitudes and beliefs. Excerpts will be printed out, and each analyst will group the excerpts into thematic categories. The extent of agreement between the analysts’ initial coding of the data will be assessed. Each analyst will define the working themes and through discussion select a final set. Data will be entered into the qualitative software program, N Vivo. The research team will use the constant comparison method and analytic memoing to identify patterns, create themes or categories, and develop theoretical insights (Strauss & Corbin, 1990).

Power Considerations

Given our sample of 165 in each of the 2 study conditions and our expectation that we will contact 80% of the sample at 12 months we should have 132 per group and a total N of 264 available for analysis for at least two time points. For tests of equality of paired differences in means for outcomes between the final interview and baseline between the two study conditions, power to detect small-to-medium effect sizes ($d=.35$) would be .82 in 2-sided tests with $\alpha=.05$.

Similar power is available for tests of equality of proportions (Cohen, 1988).

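### The plan gives criminal justice records no stated role for the roughly 20% without a 12-month interview; a prespecified record-based arrest comparison in everyone enrolled would reduce attrition bias

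*Protocol*

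**What the plan says.** The Protocol (section D, Primary Outcomes) lists parole or probation violations, arrests and days incarcerated as primary outcomes. Incarceration is to be split by cause: a new offence or a technical violation. On the source it says: "Data will be self-report but also will be confirmed using publicly available criminal justice records". The Measures table schedules these outcomes at baseline, 6 months and 1 year, which are the interview times.

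Under H3.2 the SAP expects that MICM residents "will have fewer arrests, fewer days incarcerated and lower ASI legal severity" compared with controls, tested by growth curve models. It does not mention the records. It has no rule for disagreement between the two sources, no use of records when an interview is missed, and no missing-data method specific to these outcomes.

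On follow-up, SAP Power Considerations takes 165 participants per arm and expects to reach 80% of them at the last interview. It concludes that "we should have 132 per group and a total N of 264 available for analysis for at least two time points".

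For drug use the Protocol does rank its sources: under Biological Measures, a positive urine screen overrides a report of no use. Arrests have no equivalent rule.

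**The concern.** When an outcome is collected by interview, it is missing for whoever is not interviewed. Here the outcome may drive the missingness, because a person who is rearrested or jailed can be harder to find. The Protocol anticipates this by planning to trace participants into jails and prisons (Research Interviews). The event is also common: section A reports that 37% of probationers and parolees in the earlier study had been rearrested by 6 months.

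Loss could also differ by arm. MICM participants have monthly therapist contact for 12 months and help with crises, including arrests (Structure of MICM Sessions). Controls do not. The growth models keep earlier data from people lost later. But if a rearrest after 6 months causes the missed 12-month interview, those earlier data do not remove the bias.

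Public records need no interview, and the trial already intends to consult them. Leaving their role undefined for the people not interviewed forgoes the one planned source that could show what happened to them.

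**Working it through.** **1. The plan's own figures.** Inputs from SAP Power Considerations: 165 per arm, 80% contact, d=.35, two-sided alpha .05.

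- Interviewed at 12 months: 165 × .80 = 132 per arm, 264 in total. This matches.
- Not interviewed: 330 × .20 = 66, or 33 per arm.
- Power = Φ(d√(n/2) − 1.96) = Φ(.35 × √66 − 1.96) = .81, against the stated .82. This reproduces approximately, so the stated figure makes no allowance for clustering.

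**2. Possible bias (illustration; loss rates and rates among the lost are assumptions).** Let true rearrest be 37% in both arms, so there is no treatment effect. Let loss be 25% in control and 15% in MICM, which is 20% overall. If a proportion r of those lost are rearrested, the rate seen among the interviewed is (.37 − loss × r)/(1 − loss).

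| r among the lost | Control, interviewed | MICM, interviewed | Spurious difference |
|---|---|---|---|
| 37% | 37.0% | 37.0% | 0 |
| 50% | .245/.75 = 32.7% | .295/.85 = 34.7% | 2.0 points |
| 60% | .220/.75 = 29.3% | .280/.85 = 32.9% | 3.6 points |
| 74% | .185/.75 = 24.7% | .259/.85 = 30.5% | 5.8 points |

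In this pattern the error counts against MICM. If the loss rates are swapped, the sign reverses. With equal loss and equal r in both arms, both rates are too low but the difference stays at zero.

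**3. Precision, allowing for houses.** Houses are randomised, and the SAP assumes ICC .06. Design effect = 1 + (m − 1) × .06, where m is the average number of participants per house and effective n per arm is n divided by the design effect. The SAP works with 32 houses and the Protocol randomises 70, so both are shown. The SAP's own divisor, 1 + 32 × .06, puts the number of houses where the cluster size belongs, so it is not used here.

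| Houses | n per arm | m | Design effect | Effective n | Power at d=.35 |
|---|---|---|---|---|---|
| 32 | 132 | 8.25 | 1.435 | 92.0 | .66 |
| 32 | 165 | 10.31 | 1.559 | 105.9 | .72 |
| 70 | 132 | 3.77 | 1.166 | 113.2 | .75 |
| 70 | 165 | 4.71 | 1.223 | 134.9 | .82 |

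The rows with 165 assume that the records cover all 330. Partial coverage gives values in between.

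**The case against.** **Record quality is unknown.** The documents give no jurisdiction, matching method or completeness for the records, and do not say whether they show days in custody. A source good enough to corroborate an interview may not be good enough to stand alone. A person with no record found would be counted as not arrested, which turns visible missing data into hidden misclassification. This stands. It is why the record-based analysis should sit beside self-report and come with a coverage statement.

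**Safeguards exist.** The Protocol plans 3- and 9-month locator contacts in both arms, tracing through family and friends, and interviews in custody. These lessen the problem, but the SAP still expects 20% loss. No document shows that loss will differ by arm or that those lost are rearrested more often. Both are plausible risks, not established facts.

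**Consent.** The consent content in Protocol section H describes questionnaires and interviews and does not list a record search. This stands, and it applies equally to the confirming use already planned.

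**Stronger readings that the documents do not support.** A reader might infer that:

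- *Records should replace self-report as the primary source.* That is a debatable trade-off while coverage is undescribed. Technical violations, and hence total days incarcerated, would still rest partly on interviews.
- *The analysable sample would rise from 132 to 165 per arm and power from .81 to .89.* Those power figures ignore clustering. The growth models can also use baseline and 6-month data from people missing at 12 months, so 132 is not strictly the number analysed.
- *The Protocol restricts the search to those interviewed.* It does not say so. Its wording gives a confirming role, and the SAP's silence leaves the rest open.

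**Conclusion.** The concern holds as a gap in the plan. As written, primary arrest data at 12 months are expected to be unobserved for about 66 of 330 participants, although the trial already intends to consult a source that does not depend on the interview.

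The main gain from closing the gap is less attrition bias for arrests. Its size cannot be known from the documents. Under the assumptions above, the spurious difference ranges from 0 to about 6 points of rearrest.

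The precision gain is smaller: at most about .06 to .07 in power. It rests on full record coverage, ICC .06, and d=.35 in a normal-theory comparison, which is a rough proxy for arrest counts. The case is strongest for arrests. It extends to new-offence incarceration only if the records show custody days, and it does not extend to technical violations.

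**What to change.** In the Protocol and SAP:

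1. Search the records for every enrolled participant, interviewed or not, over the same fixed windows: baseline to 6 months and 6 to 12 months.
2. Prespecify a comparison of record-based arrests in everyone enrolled, by randomised house condition and with house clustering in the model, reported alongside the self-report analysis. Add new-offence incarceration if the records show custody days.
3. State which jurisdictions and event types the records cover, and how participants are matched to them.
4. State which source prevails when self-report and records disagree, as is already done for urine screens.
5. Confirm that consent covers the search, including for people who miss later interviews.
6. Keep self-report for technical violations and total days incarcerated.

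The cost is about 66 further searches, the SAP wording and a check of the consent form. The downside is that records may miss out-of-area arrests. That such misses are equal in both arms is an assumption, which comparing the two sources by arm among interviewed participants would partly test.

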**A. Study Aims, Background and Design**

**B. Subject Population**

**C. Recruitment Process**

**D. Procedures**

**E. Assessment of Benefits**

**F. Assessment of Risks**

**G. Confidentiality**

**H. Informed Consent**

**I. Financial Issues**

## **A. Study Aims, Background and Design**

At the conclusion of 2005 one in every one hundred thirty-six adults in the U.S. was incarcerated in criminal justice institutions (Pew Charitable Trusts, 2009). When individuals on probation and parole are added, the proportion is a striking one in every thirty-two. The risk for HIV infection among criminal justice offenders is significant. Rates of infection are 4 to 10 times higher than that found in the general population (Golembeski & Fullilove, 2008). Leukefeld et al. (2009) noted that 25% of all HIV infected persons have had contact with the criminal justice system and women offenders are 15 times more likely to be HIV infected than their non-offending peers. However, offenders are under tested and under treated for HIV, which puts them and their partners at risk (Maruschak, 2004). Offenders who are currently HIV negative are at high risk for infection due to high rates of injection drug use and unprotected sex (Belenko, 2006).

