### **Summary of Inclusion/Exclusion Criteria**

We plan to recruit only offenders who are HIV+ or at high risk for HIV. Inclusion criteria will require at least one of the following: HIV+, MSM, history of injection drug use, history of sex work, and past month unprotected anal or vaginal sex with more than one partner. All potential participants will be recruited from a pool of individuals who have a history of substance dependence and criminal justice involvement, factors known to be associated with HIV infection and risk (Belenko, 2006). Over half of our potential sample will have a history of methamphetamine dependence, another high risk factor (Center for Disease Control, 2007). Offenders must be able to speak English and those who show evidence of a serious mental health disorder that would hinder their ability to provide informed consent will be excluded. Study therapists will conduct these assessments when necessary and make a determination. In addition, to be included in the study residents must agree to be randomly assigned to one of the 2 study conditions and provide some contact information that can be used to locate them for follow-up interviews.

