$\alpha_{i,h} = \vartheta_{0,h} + \vartheta_1 X_{i,h} + u_{0,i,h}$ and the random slope will be parameterized as $\beta_{i,h} = \lambda_{0,h} + \lambda_1 X_{i,h} + u_{1,i,h}$ where $X_{i,h}$ are time invariant individual-level covariates (e.g., baseline age, ethnicity) and the $u_{0,h}$ and $u_{1,h}$ are random variables that indicate unexplained variation in the random intercept and slope across individuals. To assess variability of the dependent variable across houses, both at baseline (the intercept) and over time (the slope), the random intercept of the level 1 intercept ($\theta_{0,h}$) and the random intercept of the level 1 slope ($\lambda_{0,h}$) will be parameterized as

$\vartheta_{0,h} = \gamma_{0,0} + \gamma_{0,0}Z_h + v_{0,h}$ and $\lambda_{0,h} = \gamma_{1,0} + \gamma_{1,0}Z_h + v_{1,h}$ where the Z_h are house-level variables and the $v_{0,h}$ and $v_{1,h}$ are random variables indicating unexplained variation in the average growth parameters across houses. Therefore, both individual-level and house-level variables will be incorporated into the longitudinal model to predict variability in growth parameters. In

addition to accounting for the nesting of individuals within time, the models will account for the nesting of individuals within houses which, when left unconsidered even if no house level variables Z are entered into the model, may result in underestimates of level 2 model variances u_o and u_i and therefore invalid inferences for the effects of individual-level variables on longitudinal trajectories.

Dose-Response Analysis for MMI

For participants in the MMI condition we will conduct a dose-response analysis. Our rationale draws on the case management study by Longshore et al (2005). They reported a significant relationship between the number of case management contacts with residents and primary outcome variables. We will complete a similar analysis using bivariate associations (e.g., by examining χ^2 tests and estimated correlations) and multivariate models that assess dose effects controlling for selected variables.

Analysis of Specific Aims

Aim 1: *To assess HIV testing rates, HIV risk behaviors, and utilization for HIV services at baseline, 6, and 12 months.*

H1.1 Residents receiving MMI in addition to drug free housing will have higher rates of HIV testing, higher utilization of HIV services, and fewer HIV risk behaviors than the drug free housing and resource manual condition.

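### HIV treatment engagement is scored only among people known to be positive, a group that post-randomisation testing can change, so the service-use part of H1.1 is not a comparison of randomised groups

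*Protocol*

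**What the plan says.** The Protocol's Primary Outcomes section says "We will also record self-report of HIV status and current engagement in HIV treatment services", with engagement coded yes or no "for those who are positive". The Measures table schedules HIV status, testing and treatment at all three interviews, and Aim 1 covers "utilization for HIV services at baseline, 6, and 12 months". The only biological measure is a urine screen that checks reported drug use. A participant therefore counts as positive only after being tested elsewhere, learning the result and reporting it.

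The intervention (MICM in the Protocol, MMI in the SAP) lists "addressing HIV risk, testing and treatment" among the problems it can address. H1.1 predicts that residents receiving it "will have higher rates of HIV testing, higher utilization of HIV services, and fewer HIV risk behaviors". Known infection is not needed for entry: "Inclusion criteria will require at least one of the following: HIV+, MSM, history of injection drug use, history of sex work" are alternatives, together with recent unprotected sex with more than one partner. The background says that "offenders are under tested and under treated for HIV", and the number tested for the first time is itself an outcome.

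The SAP (Analysis of Specific Aims, Aim 1) tests H1.1 in the general longitudinal model, through the treatment coefficient on rate of change. It gives no rule for who is in the engagement comparison.

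**The concern.** Being a known positive at 6 or 12 months is a consequence of testing, and testing is something MICM is meant to change. If it succeeds, infections that were undiagnosed at baseline come to light in the MICM arm and enter its denominator. Comparable infected people in control who are not tested stay out of theirs. The two groups of known positives then differ in make-up for reasons unrelated to MICM's effect on engagement, despite the Protocol's intent-to-treat commitment.

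The slope-based test does not remove the problem. A newly diagnosed person has no baseline engagement value and enters only at follow-up, so that person bears directly on the change being compared. A difference in either direction could not be attributed to better or worse engagement in care. Only the service-use component of H1.1 is exposed. HIV testing and risk behaviour are not limited to those who are positive.

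**Working it through.** **The plan's own figure.** The documents give no figure for treatment engagement. The nearest is in Power Considerations: .82 for d = .35 with 132 per group, two-sided α = .05. Check: .35 × √(132/2) = 2.84; 2.84 − 1.96 = 0.88; Φ(0.88) ≈ .81. That is reproduced to within rounding, but it uses all 132 per arm and not the HIV-positive subset.

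**Inputs.** 132 per arm is from the SAP. Everything else is assumed, because the documents give no HIV prevalence, undiagnosed share, testing rate or engagement rate:
- K, known positives at baseline: 5%, 10% or 20% of 132
- U, undiagnosed positives: 1%, 2% or 5% of 132
- t, share of U tested by follow-up: 30% control v 60% MICM, or 40% v 80%
- eK and eN, engagement among known and newly diagnosed positives

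**Formula, per arm.** Apparent engagement = (K·eK + U·t·eN) / (K + U·t).

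**Worked case.** K = 13.2, U = 6.6, t = 40% v 80%, eK = 70% and eN = 30% in both arms, so there is no true effect on engagement.
- Control: (9.24 + 2.64 × 0.30) / (13.2 + 2.64) = 10.03 / 15.84 = 63.3%
- MICM: (9.24 + 5.28 × 0.30) / (13.2 + 5.28) = 10.82 / 18.48 = 58.6%

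MICM appears 4.8 points lower, although more of its participants are diagnosed and in care (10.82 v 10.03).

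**All combinations of K, U and t.**

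| Engagement assumed | Apparent difference, MICM − control (points) |
|---|---|
| eK 70%, eN 30%, both arms | −6.3 to −0.6 |
| eN = eK, both arms | 0 |
| eK 50%, eN 80%, both arms | +0.4 to +4.8 |
| Control 70%/30%; MICM 5 points higher in each subgroup | −1.3 to +4.4 (negative only at K 5%, U 5%) |
| Control 70%/30%; MICM 10 points higher in each subgroup | +3.7 to +9.4 |

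**Precision.** In the worked case the 95% half-width is 1.96 × √(.586 × .414/18.48 + .633 × .367/15.84) ≈ 33 points, ignoring clustering by house. The distortion is small beside that.

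**With the denominator fixed.** Among baseline positives, the arm difference equals the true effect assumed in that group (0, 5 or 10 points). Diagnosed-and-in-care over all 132 per arm, with no engagement effect, differs by U × (difference in t) × eN / 132. With eN at 30% or 50% this runs from 1% × .30 × .30 ≈ +0.1 points to 5% × .40 × .50 = +1.0 points. It is never negative, and it reflects the extra case finding.

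**Power of the fixed comparison.** K is about 7 to 26 per arm. For 50% v 70% engagement, power = Φ[(0.2 − 1.96√(0.48/n)) / √(0.46/n)]. This gives 11% at n = 6.6, 18% at 13.2 and 31% at 26.4, again ignoring clustering.

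**The case against.** The strongest reply is that the Protocol's sentence says who is asked the treatment question, not how it will be analysed. Asking it of people not known to be positive would make no sense. H1.1 is worded for residents and HIV services, and neither document equates that with this one item. Scoring engagement over all residents, or by baseline status, would also fit the text. It stands that a denominator at each interview is inferred. It does not dispose of the point. This is the only HIV service-use item named, the stated scoring rule leads most directly to current positives, and nothing in the SAP directs otherwise. The Services Received measure gives healthcare as an example but does not mention HIV services.

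A reader might infer something stronger: that the two parts of H1.1 pull against each other, so that the better arm will show lower engagement. The documents do not support that. It needs newly diagnosed people to be less engaged than known positives, which neither document says. MICM is also meant to link clients to services and help them use them, which could offset it. Small examples that reverse the sign depend on what is put in. Take 12 of 15 known positives in care in each arm (80%), and two new diagnoses in MICM only. MICM then scores 13/17 = 76% or 12/17 = 71%, according to whether one or neither is in care. This allows control no new diagnoses and MICM no benefit among known positives. If one of the three known positives out of care also enters care, MICM scores 14/17 = 82% and the reversal is gone.

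It is also fair that small numbers are the larger problem for this outcome, and that changing the denominator does not solve it.

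**Conclusion.** The point holds as a weakness in how the comparison is formed, with bias of unknown sign. On the natural reading, the service-use part of H1.1 conditions on a status that the intervention can alter, and no analysis rule corrects this. With no true engagement effect, the assumed ranges give distortions from −6.3 to +4.8 points. A true gain of 5 points changes sign only in the most extreme corner tried, and a true gain of 10 points is diluted but never reversed. These sizes rest wholly on assumed rates and on the inferred denominator. With perhaps 7 to 26 baseline positives per arm, intervals will be wide under any definition, so a statistically clear but wrong result is not the main risk. The risk is a reported difference that has no clear meaning. This is a cheap improvement, not a threat to the trial's other conclusions.

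**What to change.** In the Protocol's Primary Outcomes section and the SAP's text for H1.1, specify:

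(a) Treatment engagement is compared between arms at 6 and 12 months among participants who reported being HIV-positive at baseline.

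(b) The number diagnosed and in care is reported by arm over all participants. Among all those not reporting positive status at baseline, the number newly diagnosed and the number newly diagnosed and in care are also reported by arm. The denominator is that whole group, not only those diagnosed.

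(c) These results are presented descriptively with confidence intervals, given the small numbers.

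The cost is wording and a few extra table rows, because status, testing and treatment are already scheduled at all three interviews. The drawback is that newly diagnosed people leave comparison (a). They are counted in (b), where extra case finding is shown separately from engagement among those already known to be positive. Power for (a) stays low.
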